Determine whether NutraStem® in combination with an exercise stimulus will cause increased human peripheral blood sample levels of CD34+ and CD133+ adult stem cells and whether these stem cells display more protection against oxidative stress.

B. Background and Significance

A stem cell is a specialized kind of cell that has a unique capacity to renew itself and to give rise to specialized cell types. These cells are found in many organs of the adult human including bone marrow, peripheral blood, umbilical cord blood, spleen, tooth pulp, adipose tissue, and brain. Stem cell research is currently a popular subject in the media and science (1). While stem cell therapies have been promised to offer important new treatments for a wide variety of illnesses, these therapies remain controversial and may take years to reach the medical market place due to the lengthy and costly regulatory requirements. Fortunately, a growing body of evidence suggests that there are numerous stem cells continually being produced within the human body throughout the lifespan. These stem cells are located in many different tissues and can become or "differentiate" into virtually any cell type within the body. Internal or endogenous stem cells are crucial to the body's ability to repair itself of degenerating tissues, or to replace cell populations, such as those destroyed by injuries, diseases, disorders, or treatments such as chemotherapy. Healthy stem cells are vital for the body's own natural regeneration and repair mechanisms to function. During natural aging, adult stem cells are known to have a reduced restorative capacity (2, 3) resulting in a reduced ability of the body to heal itself. However, a rapidly growing body of literature now indicates that certain nutrients, vitamins, and flavonoids could have important roles in the proliferation and replacement of stem cells required for healthy self-renewal of mature cells in the blood, brain, and other tissues (4-7). Thus, it appears possible to use certain natural products, either alone or synergistically, for the treatment of conditions where the stem cell replacement appears warranted.

C. Preliminary Studies

Preliminary studies establishing the effect of NutraStem® to increase proliferation of human adults stem cells and to demonstrate a homing effect in

[figure not shown]
[figure not shown]

Figure 2. Protection of bone marrow cells in culture in mice fed NT-020 for 2 weeks prior to bone marrow collection. Cells were grown in culture for 3 days and then challenged with varying doses of H₂O₂. In mice receiving either a low or high dose of NT-020 there was significant protection against oxidative damage to the cells.

models of injury.

We have examined the effects of combining different nutritional supplements together with the goal of finding synergistic effects of components to increase actions on the proliferation of progenitor cell populations and to reduce inflammation and oxidative stress. We found that a combination of blueberry, green tea (EGCG), carnosine and Vit D3 (known as NT-020 or NutraStem®) had a synergistic effect to promote proliferation of hematopoietic stem cells in culture (6). In figure 1 is shown the data for CD34+ stem cells and similar data is observed for bone marrow and CD133+ cells. To determine if this proprietary blend would protect cells *in vivo* NT-020 was then administered to mice for 2 weeks and bone marrow cells removed from the mice and cultured for 3 days (without further NT-020) then exposed to H₂O₂ to induce oxidative stress. It can be seen that the bone marrow cells from mice treated with either a high or low dose of NT-020 showed protection from the H₂O₂ insult when cell death was measured by LDH release (Fig. 2). The low dose is equivalent on a mg/kg basis to the human dose available commercially as a dietary supplement, the high dose is actually closer to the biologically equivalent dose as the metabolism of the mouse is approximately 10X higher than human, thus the 135 mg/kg dose is biologically similar to the human dose for expected blood levels of the active ingredients to be used in this study. This also demonstrates that the effect of NT-020 is to modify cell function, perhaps through an epigenetic mechanism as the effect to increase resistance to H₂O₂ was present 3 days after exposure to NT-020 as the cells were only treated *in vivo* and NT-020 was not included in the cell culture media.

The next study examined the formulation of NT-020 in an animal model of stroke to examine efficacy in a disease model where we had previously shown that blueberry showed a 50 % neuroprotection from a middle cerebral artery occlusion (MCAO) 60 minute occlusion followed by reperfusion and measured as the size of the infarct when rats were fed blueberry as 2% of the diet beginning 30 days prior to stroke. In this study we examined if the NT-020 would also be neuroprotective and if

[figure not shown]

Figure 3. Area of damage following a 60 minute occlusion of the middle cerebral artery (MCAO). Rats treated with NT-020 show 70% smaller lesion than vehicle treated rats. see Yasuhara et al, 2008

this correlated to an increase in neurogenesis. As can be seen in figure 3 there was a 70% protection of damage following the stroke at 14 days post-stroke in the NT-020 treated animals (7). Animals were treated for 2 weeks prior to stroke (MCAO 60 minute occlusion) and then treatment was not continued after stroke, again demonstrating that the effect outlasts treatment suggesting a change at the cellular level. The next figure (4) demonstrates that this was accompanied by an increase in neurogenesis in both the stem cell niche of the subventricular zone (SVZ) and in the damaged tissue of the striatum. Appropriate controls were performed to analyze double staining of BrDU with doublecortin and the majority of cells labeled with BrDU in the NT-020 treated rats were double labeled with doublecortin, however in the vehicle treated rats the majority of the cells were double labeled with GFAP suggesting a shift of cell fate towards the neuronal lineage following stroke in the NT020 treated rats. Furthermore the data also suggests (but cannot at this time prove) that the homing of the cells from the neurogenic niche (SVZ) to the damaged tissue (striatum) was increased by the treatment. Overall the data show that the combination of blueberry, green tea (EGCG), carnosine and Vitamin D3 is a potent neuroprotective agent that increases neurogenesis. One additional point with this data is that the amount of blueberry used for the individual treatment would be equivalent to about 20 grams of dried blueberry powder per day for human consumption. The synergistic actions of the 4 ingredients combined together showed neuroprotective effects at 1 gram per day human equivalent dosage, thus a reasonable amount of capsules to consume (2 per day) as opposed to 40 capsules per day for the blueberry alone to get an equivalent effect (8).

NT-020 increases neurogenesis in aged rats and improves performance on a Morris water maze.

[figure not shown]

Figure 4. Mean counts of BrDU positive cells in the subventricular zone (SVZ), the neurogenic niche, or the striatum, the damaged area. NT-020 increases BrDU labeling in both regions, with the largest effect observed in the striatum. For specific methods see Yasuhara et al Rejuvenation Res. 11:201-214, 2008.

[figure not shown]

Figure 5: Upper left shows quantification of doublecortin (DCX) positive neurons in the granule cell layer with inset on the side for young (top), aged (middle) and aged treated (bottom) at low and higher power. Upper right shows quantification for MHCII positive cells – presumably microglia with insert of images as for DCX. Differences were significant at *** p<0.001 or ** p<0.01 using Bonferroni post hoc following one way ANOVA.

As aging has been shown to reduce proliferation of stem cells in many of the stem cell niches of the body we extended our studies to aging models. We examined the effect of NT-020 to improve Morris water maze performance and neurogenesis in the hippocampus and subventricular zone of 20 month old F344 rats (9). Aged (20 month old) male Fischer 344 rats were treated with 135.0 mg/kg per day (n = 13) of NT-020 by oral gavage. Young (3 month old) (n = 10) Aged (20 month old) (n = 13) control male Fischer 344 rats were treated with water by oral gavage. All groups were treated for a period of 4 weeks. We examined learning on a Morris water maze and observed an improvement in memory performance (see Acosta et al, 2010). We next examined proliferation of neural progenitors and microglial phenotype with the diet treatment. Using the cell cycle-regulating protein (Ki67), doublecortin (DCX) and OX6 (MHCII) antibody markers, cell proliferation, neurogenesis and microglial activation were estimated in the dentate gyrus (DG) of young and aged animals. Cell proliferation was also examined in the subventricular zone (SVZ). Decreased number of OX6 MHC II positive cells, increased neurogenesis, and increased number of proliferating cells were found in rats treated with NT-020 in comparison with aged control rats (Figure 5).

D. Investigator Experience

[name]. is currently Chair of the department of Pharmacology & Neuroscience, the Director for Research for the Center FOR HER (a women's health center at UNTHSC), and serves as the interim Director of the Institute for Aging and Alzheimer's Disease Research at the University of North Texas Health Science Center. He has had a long-standing interest in the neurobiology of steroid hormones, particularly within the context of brain aging and Alzheimer's disease. He has served as PI of several research grants (including those from the NIH), including a multi-investigator Program Project grant (P01). He continues to successfully administer these projects (e.g. staffing, execution/direction of experiments, managing of budget, etc.), collaborate with other researchers, and ensures the dissemination of his findings through peer-reviewed publications.

E. Experimental Design and Methods

This will be a randomized double blinded placebo controlled trial of a nutraceutical preparation. Up to 60 men and women between the ages of 50 and 70, and generally healthy will participate in this study. All clinical study procedures will occur in the

clinical research lab in CBH 503. This includes informed consent, phlebotomy, blood pressure monitoring, and exercise stimulus. Up to 30 participants will receive the nutritional supplement and up to 30 will receive placebo.

Potential participants will be screened by telephone and have the study explained to them in detail. If they qualify and choose to participate they will come in for the first of three visits. Informed consent will be obtained and demographic information collected. Information requested on the demographic form includes ethnicity, income, education, marital status, smoking and alcohol use, and exercise habits. Next they will have blood pressure checked and if not within parameters they will be dropped from the study and informed that they need to follow up the abnormal result with their health care provider. They will receive \$20.00 partial compensation for their time. Next a finger stick blood glucose check will be done to rule out diabetes. If their result falls out of the specified parameter range they will be dropped from the study and informed that they need to follow up the abnormal result with their health care provider. They will receive \$20.00 partial compensation for their time. Those that pass these screening tests will have 15 to 25 cc's of peripheral blood (serum) collected by the study coordinator via venipuncture while at rest. They will then stretch for 2 minutes (60 seconds marching in place followed by 10 toe touches) followed by accelerating treadmill walking exercise. The exercise intervention will consist of a 15 minute period of walking on a treadmill. The treadmill will not be inclined during the intervention. The participants target heart rate will be determined by deducting their age from 220. They will start walking on the treadmill at a speed of 1.7 mph and the speed will be titrated as indicated to keep their heart rate at 50 to 90% of target. Heart rate will be monitored via the pulse oximetry feature of the Welch Allyn vital signs monitor. Blood pressure will be measured every 3 minutes during the exercise intervention and until they have returned to baseline (within 10 points) following cessation of the exercise protocol. The test will be stopped for any participant complaint of chest pain, excess fatigue, difficulty breathing, a blood pressure reading of more than 180/94, or a participant request. If symptoms increase or do not completely resolve with 15 minutes of rest the study coordinator will call 911 (through campus police) to activate the EMS response. If symptoms resolve completely within 15 minutes participants will be withdrawn from the study and advised to follow up with their health care provider. Any participant unable to complete the exercise intervention for any reason will be withdrawn from the study.

The exercise intervention is no more intense than what most participants would encounter walking during their normal day-to-day activities. The participants will be closely monitored and the intervention stopped for any subjective or objective evidence of discomfort. Participants involved in this study will have been screened for any medical conditions that would increase their risk of any negative effects from the exercise intervention.

Five to fifteen minutes after the exercise intervention has been completed blood will again be collected in exactly the same manner as the resting sample. Participants will then receive a 2 week supply of either NutraStem or placebo and will be advised to take one tablet every morning and evening before meals for the next 2 weeks. Participants will be advised to bring their empty pill containers to their next session so we can confirm they are taking the supplement as required. Those that complete the 1st session will receive \$40.00 compensation. If the participant is unable to complete any portion of the visit activities at any visit they will be withdrawn from the study due to their

inability to complete the study. All visit activities will be recorded in detail on the visit session record.

The second visit will occur 2 weeks later and include a blood pressure check, an at rest blood draw, the exercise intervention, and then a repeat blood draw five to fifteen minutes after completion of the intervention. Participants will then receive a 2 week supply of either NutraStem or placebo and will be advised to take one tablet every morning and evening before meals for the next 2 weeks. Participants will be advised to bring their empty pill containers to their next session so we can confirm they are taking the supplement as required. If the blood pressure is outside of the specified range they will be dropped from the study and no blood collection or study intervention will take place. They will receive \$20.00 compensation for the visit. Those that complete the 2nd session will receive \$60.00 compensation.

The third visit will be the same as the second visit. If the session cannot be completed due to failed blood pressure screen participants will receive \$20.00. All participants that complete the 3rd session will receive \$80.00.

SESSION	ACTIVITIES	VISIT LENGTH	COMPENSATION
VISIT 1	informed consent, demographic information collected, BP screening, diabetes screening, resting blood draw, exercise intervention, post exercise intervention blood draw, receive NutraStem or placebo	40 to 80 minutes	\$40.00 * \$20.00 if unable to complete session for any reason
Visit 2	resting blood draw, exercise intervention, post intervention blood draw	45 minutes	\$60.00 * \$20.00 if unable to complete session for any reason
Visit 3	resting blood draw, exercise intervention, post intervention blood draw,	45 minutes	\$80.00 * \$20.00 if unable to complete session for any reason

Blood Analysis:

A 10ml Lavender top with EDTA tube of collected blood will be processed for MNC's and designated for flow cytometry to measure the stem cells including CD34+ and CD133+ cells at all blood draw time points. [name] will complete this portion of the analysis. A 5 ml SST tube will be collected for a lipid panel on the 1st blood draw of each session and delivered by the coordinator to Quest Lab for analysis. One additional tube of 5 cc's will be processed for serum measurements of biomarkers of inflammation and oxidative stress by the sponsor. These measures (IL1 β , IL4, IL6, hsCRP) will be completed by the sponsor. De-identified serum samples will be stored by [name] lab in a locked -80 freezer on the 5th floor of CBH until the sponsor specified time points of the study and then shipped to the sponsor following IATA Dangerous Goods Regulations by [name] lab personnel.

Blood sample collection tubes will be pre-labeled by the pharmacist doing the study drug/placebo randomization. The following randomization system will be used for the samples collected during this study:

Identifier (randomized to active ingredient or placebo)	Subject number	Study	Visit	Blood Draw	Description of Blood Draw
JKSB	01	01	01		Pre-exercise
JKSB	02	02	02		Post-exercise
JKSB	03	03	01		Pre-exercise
JKSB	03		02		Post-exercise
JKSB	04			01	Pre-exercise
				02	Post-exercise

Therefore, subject 17 on visit 3 for the post-exercise blood draw would be coded as:
JSKB170302

Subject 5 for visit 1 and pre-exercise blood draw would be coded as:
JSKB050101

Use of Blood Samples and Related Data For Other Research Purposes In the consent form, subjects will be asked if they agree to the transfer of some of their blood and related research data to other researchers for analysis and testing that may not related to this study (no additional blood will be drawn). This is voluntary, and if subjects do not agree to this transfer, they can still participate in the main study. Blood samples and related data will only be prepared for transfer if the subject meets criteria that is specified by the other researcher in his or her protocol. Prior to transfer, study personnel will de-identify the blood sample and any related data. The specimen container and related data will be labeled with a code that does not identify the subject or contain any personal information about the subject in order to protect his or her confidentiality. Any remaining blood that is not prepared for transfer will be destroyed after the testing for this study is complete. Once transferred, the blood sample and related data will be stored indefinitely by the other researchers. Researchers requesting blood samples and related data from subjects in this study must obtain IRB approval for their study before the PI will initiate the transfer of any samples and related data. Documentation that IRB approval has been obtained will be requested and maintained in the PI's study files. The PI will also provide a letter to the OPHS/IRB that indicates his agreement that the other researcher can use his subject's samples and related data for their research.

Randomization Process (drug):

[name], UNT Pharmacist, will create a randomization assignment based on Meinert et al. (10). He will label small envelopes with the STUDY number (Example USF Trial: Subject 1). In this small envelope will be a piece of paper with either the words 'CASE' or 'PLACEBO' or other analogous wording.

These envelopes will be maintained by UNTHSC pharmacist, [name]. He will keep these confidential.

The pharmacist will keep the product and placebo in separate boxes. The appropriate product/placebo will be placed in a small paper grocery bag and the outside of the bag will be labeled with the STUDY ID NUMBER (Example USF STUDY 12). When the research coordinator is ready for the product/placebo, she will take the bag from the designated area and deliver it to the subject with appropriate instructions.

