All quantifiable results will be expressed as mean \pm sem and will be analyzed using repeated measures Analysis of Variance (ANOVA). All post-hoc tests will be conducted using a Scheffè test. Only de-identified data will be sent to the sponsor for completion of data analysis. Subject data will be maintained by the study coordinator in a locked cabinet in CBH 508. Electronic databases will be maintained on a password protected computer. The study coordinator will create and maintain a password protected Excel master list that will contain study participants names, demographic information, study ID, and information recorded during the study sessions. Flow Cytometry results will be submitted to the research coordinator and forwarded from her to the sponsor. Data forwarded to the sponsor will be de-identified.

F. Human Subjects

Up to 60 men and women, generally healthy, age 50 to 70 with no debilitating (defined as having a chronic disease or condition that has severely limited activities of daily living, normal function, or ability to live an active life or injury). The study coordinator will explain the purpose of the study and describe all visit activities to potential participants. If they are still interested in the study they will be asked questions about their health to determine whether they are able to safely participate in the study. The “screening script” is a written tool based on the inclusion & exclusion criteria that will be used to screen all potential participants.

Inclusion Criteria

- Men or women who are 50 to 70 years of age, inclusive, at the baseline visit.
- Ability to do 15 minutes of treadmill walking exercise.
- Generally healthy

Exclusion Criteria

Subjects who meet any of the following exclusion criteria are not eligible for participation in this clinical research:

- Men and women less than age 50 or more than age 70
- Self reported history of difficult veins/difficulty obtaining blood samples
- Participated in more than 2 sessions per week of strenuous exercise in the last month
 - Are unwilling to follow the procedures of the trial, such as making visits or taking the supplements when asked to;
 - Are unable to tolerate the ingredients in NutraStem® or placebo, or who self report food allergies

- Have unintentionally lost or gained 10 or more pounds of body weight in the last 3 months;
- Have an acute illness (such as a severe cold or flu) or have been hospitalized within the past month.

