II. Recruitment Materials (ads, flyers, emails, etc.) to be used in this Study

III. Study Documents (questionnaires, survey instruments, clinical trial protocol, investigator's brochure, etc.)

IV. Evidence of Human Subject Training for ALL Key Personnel listed in the protocol.

V. Conflict of Interest Form, completed and signed by EACH Key personnel listed in the protocol.

IRB APPROVED
JAN 04 2013

University of North Texas
Health Science Center

**Healthy Adults
age 50 to 70 are
needed for a clinical
research study
investigating the effect
of light exercise and
an investigational
dietary supplement on
your blood stem cells**

Researchers at the University of North Texas Health Science Center are investigating whether a dietary supplement combined with light exercise will increase production of stem cells. You may be eligible to participate in this study if:

- You are ages 50 to 70 years old
- You are generally healthy
- Able to walk for 15 minutes

IRB APPROVED

JAN 04 2013

University of North Texas
Health Science Center

Compensation is provided

Study conducted by The University of North Texas
Health Science Center

For more information please call:

[contact]

[contact]

JAN 04 2013

University of North Texas
Health Science Center

Screening script

How may I help you? If calling about the study;

May I ask your name?: _____

How did you hear about the study? _____

We are running a 4-week study (clinical trial) on normal, healthy people to determine if taking a supplement will help the body produce a very specific type of white blood cells. These are called 'adult stem cells'.

You must be between the ages of 50 and 70 and be in good health with the ability to ride walk on a treadmill at a moderate pace for 15 minutes.

If you choose to enroll in the trial you will be randomized (assigned) to take either the real product or a look-alike placebo (fake-pill).

You take the assigned capsules twice a day for a total of 4 weeks. Every two weeks you will show up to the Clinic and go through an exercise period (for a total of 3 visits).

This consists of having a blood draw before exercise. The exercise consists of a total of 15 minutes walking on a treadmill. Every three minutes the grade will increase slightly. We will be careful not to make the exercise too difficult for you. A few minutes after the completion of the exercise, we will take another blood draw. This will conclude your exercise for the day with us.

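### The objective names no comparator and the analysis names no between-arm contrast, so a rise common to both exercising arms is not excluded as evidence for the product

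*Combined protocol and SAP*

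**What the plan says.** The objective, which opens the protocol, reads: "Determine whether NutraStem® in combination with an exercise stimulus will cause increased human peripheral blood sample levels of CD34+ and CD133+ adult stem cells". Its operative words, "in combination with an exercise stimulus will cause increased", come with no comparator, time point or contrast. The recruitment flyer puts the aim in the same combined way, asking whether "a dietary supplement combined with light exercise will increase production of stem cells".

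Section E, Experimental Design and Methods, describes the design: "This will be a randomized double blinded placebo controlled trial of a nutraceutical preparation". On allocation it says "Up to 30 participants will receive the nutritional supplement and up to 30 will receive placebo". The visit descriptions in that section give every participant a resting draw, the treadmill walk and a post-exercise draw at each of three visits, with no distinction by arm. At visit 1 the walk and both draws come first; only afterwards "Participants will then receive a 2 week supply of either NutraStem or placebo". The Blood Analysis text has CD34+ and CD133+ measured at every draw, so each person contributes six values per marker.

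The Data Analysis/Data Monitoring paragraph says that all quantifiable results "will be analyzed using repeated measures Analysis of Variance (ANOVA"), and then "All post-hoc tests will be conducted using a" Scheffé test. It does not name arm as a factor, an arm-by-time interaction, a primary contrast, an alpha level or a rule for success.

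**The concern.** The layout is 2 arms by 3 visits by 2 draws. A repeated measures ANOVA on it produces several effects, and the plan does not say which one bears on the product. Read literally, the objective could be answered by a rest-to-post rise pooled over both arms, by a drift across visits, or by a pre/post pair inside the NutraStem arm. None of these separates the product from the exercise or from time. The pooled draw effect even includes visit 1, when nobody has taken anything.

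Two things are at stake. An exercise or time effect could be reported as a finding about NutraStem with exercise when placebo with exercise does the same. And the comparison that randomisation was set up to support, if it is reached only as a post-hoc test, has to pass a stricter threshold than it would as a planned contrast. Alpha correction does not cure the first problem: a true exercise effect credited to the product is a wrong attribution, not a chance finding.

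**Working it through.** The documents give no alpha, power, effect size or SD, so there is no stated figure to reproduce. The inputs from the documents are 30 per arm (the stated maximum), 3 visits and 2 draws per visit. Two-sided alpha of 5%, the size of the exercise rise and the same-day correlation are assumptions.

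**1. Which contrast isolates the product.** Let E be the rest-to-post rise due to exercise and P the product's addition to it. At visit 3 the expected rise is E + P on NutraStem and E on placebo.
- Within the NutraStem arm: E + P, which is positive when P = 0 and E > 0.
- Between arms: (E + P) − E = P.

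Taking the change from visit 1 also removes each person's product-free baseline. The same subtraction works for resting levels, where it removes any time trend shared by the arms. In a simulation with P = 0 (20,000 runs, 30 per arm, one visit), the between-arm test was significant in 4.7% to 5.2% of runs whatever the exercise effect. The pooled draw effect was significant in 34%, 63%, 97% and 100% of runs for exercise effects of 0.2, 0.3, 0.5 and 0.8 SD of the change.

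**2. Power for the between-arm comparison, by route.** Take an effect with noncentrality 1.96 + 0.84 = 2.80, the usual value for 80% power.
- Planned contrast: critical t on 58 df is 2.00; power about 80% (79% by exact noncentral t).
- Omnibus arm-by-visit F: numerator df (2 − 1)(3 − 1) = 2, error df 58 × 2 = 116, critical F 3.07, λ = 2.80² = 7.84; power about 70%.
- Scheffé, arm-by-visit family: critical value √(2 × 3.07) = 2.48; power about 63%.
- Scheffé, arm-by-occasion family (six draws): numerator df (2 − 1)(6 − 1) = 5, error df 58 × 5 = 290, critical value √(5 × 2.245) = 3.35; power about 29%.

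The 70% assumes that the arm difference at visit 2 lies midway between those at visits 1 and 3. If the whole effect is already present at visit 2, the sum of squared deviations of (0, 1, 1) is 2/3, against 1/2 for (0, ½, 1). Then λ = 7.84 × (2/3)/(1/2) = 10.45 and the omnibus power is about 82%. The Scheffé figures for the visit 1 to visit 3 contrast do not depend on this.

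For scale, 80% power at 30 per arm needs an arm difference of about 0.73 SD of the outcome compared; a difference of 0.5 SD has 49%.

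**3. Comparing within-arm p-values when the product is inert.** For a rise of δ SD of the level and same-day correlation r, the standardised change is dz = δ/√(2(1 − r)). Let p be the chance of a significant upward paired t test with n = 30 (29 df, noncentrality dz√30). The chance of significance in NutraStem but not in placebo is p(1 − p).

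| δ | r | dz | p | p(1 − p) |
|---|---|---|---|---|
| 0.2 | 0.7 | 0.258 | 0.277 | 20% |
| 0.2 | 0.8 | 0.316 | 0.388 | 24% |
| 0.2 | 0.9 | 0.447 | 0.658 | 22% |
| 0.3 | 0.7 | 0.387 | 0.536 | 25% |
| 0.3 | 0.8 | 0.474 | 0.709 | 21% |
| 0.3 | 0.9 | 0.671 | 0.944 | 5% |

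The range is 5% to 25%. It falls at the high end because both arms then tend to be significant.

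**The case against.** The strongest reply is that the trial is randomised and placebo-controlled, with identical exercise in both arms, so a comparison with placebo is plainly intended and its omission from a one-sentence objective is loose wording. Much of this stands. Shared exercise is not a design flaw; it is what lets the product effect be separated. A reader might infer that a rest-to-post rise in the NutraStem arm counts as success. The documents do not support that, because they define no success rule at all. The flyer is recruitment text and sets no analysis. What survives is that neither the objective nor the analysis paragraph commits to the comparison that the design permits.

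A second reply is that unadjusted within-arm tests are not in the plan, since a pre/post pair inside one arm would itself go through Scheffé. That is fair. For a 0.3 SD rise, the 54% to 94% in the table (correlation 0.7 to 0.9) falls to about 37% to 88% at a critical value of 2.48, and to about 2% to 25% at 4.48, the value if all 12 cell means form one family. The 5% to 25% pattern therefore describes what happens if within-arm p-values are compared without adjustment, not what the stated plan would produce. The pooled draw effect is an ANOVA main effect and is not reduced by Scheffé, but it is not a NutraStem-arm result either.

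A third reply is that if arm is in the model, the arm-by-visit interaction is an omnibus F test and Scheffé governs only the follow-up. This also stands, so it would be wrong to infer that the randomised comparison is necessarily the one tested with least power. The Scheffé loss applies only if the comparison is made post hoc.

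**Conclusion.** The point holds as a gap in the objective and the analysis plan, not in the design. Exercise, draw and visit effects are common to both arms, and nothing in the text prevents them from being offered as evidence for the product. A planned between-arm contrast in change from visit 1 to visit 3 removes them. It keeps about 80% power where the omnibus arm-by-visit F has about 70% (if the effect builds evenly over visits), and Scheffé has about 63% or 29% depending on the family. Those figures assume two-sided 5% and a full 30 per arm; fewer completers would lower the power of every route.

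That exercise raises these cells at all is an assumption, since the documents give no figure for the response, and the 5% to 25% rests on the assumed rises and correlations shown. The change is worth making before analysis, but the trial remains able to answer its question.

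**What to change.** 1. Reword the objective as NutraStem plus exercise compared with placebo plus exercise.
2. In Data Analysis/Data Monitoring, state that a product claim rests only on the arm difference in change from visit 1 to visit 3, tested as a planned contrast outside Scheffé, for (a) the resting level and (b) the post-minus-pre-exercise change.
3. Two outcomes for each of CD34+ and CD133+ make four tests. State the alpha, and either name one as primary or split alpha across them; an equal split of an assumed 5% gives 0.05/4 = 0.0125 each. With 80% power already requiring about 0.73 SD at the full 5%, naming one primary test costs less power.
4. Keep Scheffé for unplanned comparisons.
5. Report within-arm draw and visit changes as exercise or time effects only.

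The cost is a few lines of text, with no added participants, visits or assays. The downside is that within-arm rises can no longer be presented as product findings. Other between-arm contrasts would also be valid; what matters is that one is named in advance.
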